3.2. Subject Restrictions

Lifestyle/ Dietary

During the entire study (screening – Last Subject Last Visit (LSLV));

- 1. Subjects must not take holiday outside of their home country.
- 2. Subjects must avoid water sports including sailing, diving, swimming and winter sports including skiing and snowboarding.

Medications and Treatments

On the day of site visit;

- 1. Subjects must cleanse their face with water (only).
- 2. Subjects must not apply any other cosmetic or medicated treatment on the face, including the test products provided.

During the entire study (screening – LSLV);

- 1. Subjects must not apply any other cosmetic or medicated treatment on the face, other than the test products provided.
- 2. Subjects may continue to wear their current brand of mascara and lipstick but must not use any facial cosmetics (e.g. blusher, foundation, tinted moisturiser, eyeshadow).
- 3. Subjects must not change their brand or usage of shampoo, shower gel, hand soap and other cosmetic products otherwise used on the body.
- 4. Female subjects of child-bearing potential must use effective contraception.
- 5. Subjects must not change any hormonal treatment or contraception that they may be receiving and must have used the same contraception for 3 months prior to screening.
- 6. Subjects must not undergo any aesthetic, cosmetic or dermatological

Document Name	Rainbow Clinical Protocol.doc		
Туре	Version	Document Identifier	Effective Date
eldo controlled	4.0; Most-Recent; Effective; CURRENT	090032d580d464b0	23-May-2017 08:33:00
Reason For Issue	Auto Issue		

- treatment in the treatment area (face or eyes)
- Subjects must not use any study prohibited medication as specified in the exclusion criteria.
- 8. Subjects must avoid photodynamic therapy, laser therapy, microdermabrasion for acne.
- 9. Subject must avoid sunbathing, ultraviolet (UV) treatments and tanning salons.
- 10. The use of sunscreen on the face is not permitted.

3.3. Type and Planned Number of Subjects

Approximately 200 female subjects aged 18-45 with self-assessed sensitive skin and a minimum of $\frac{10}{8}$ and a maximum of 25 facial blemishes (papules and pustules, excluding the nose) will be screened to randomise 132 healthy subjects, to ensure approximately 40 subjects in the test product regimen, 40 subjects in the no treatment regimen and 40 subjects in the positive control regimen complete the study (Assuming a 10% dropout rate). Randomisation will be stratified by age (<21 years old, \geq 21 years of age).

The sample size was based on clinical considerations. In a previous study of a cosmetic product, counts of papules and pustules decreased from a baseline mean of 27.6 to a mean of 13.5 at Week 8 (ref. Shalita 1995 IJD). With 40 subjects in both the test product and no-treatment regimens, a difference between groups at least 60% the magnitude of the standard deviation (assumed equal for both groups) would be detectable at two-sided alpha=0.05 with approximately 80% power.

3.4. Study Design and Dose Justification

This proof of concept study is part of a broader development program to bring to market a range of cosmetic products targeted at female adults with sensitive, blemish-prone skin. The study is designed as a randomised, parallel-group, evaluator-blind, positive and no-treatment controlled, single-site, clinical study to evaluate the cosmetic benefits provided by 8 weeks of twice-daily topical application of a developmental moisturising cream with niacinamide in healthy subjects with sensitive, oily, blemish-prone skin.

For the purpose of this clinical study a steady state approximation is assumed, i.e. that the rate at which new blemishes appear is equal to the rate at which blemishes disappear. As this product is designed to prevent new blemishes from forming by

Document Name	Rainbow Clinical Protocol.doc		
Туре	Version	Document Identifier	Effective Date
eldo controlled	4.0; Most-Recent; Effective; CURRENT	090032d580d464b0	23-May-2017 08:33:00
Reason For Issue	Auto Issue		

ensuring the skin is well moisturised to facilitate efficient desquamation, it is expected that there will be a preventative effect on the rate at which new blemishes appear. To account for natural fluctuations in blemish counts, subjects will only be enrolled into the washout phase if they have a minimum of 10 8 and a maximum of 25 facial blemishes (papules and pustules), excluding the nose.

NOTE: ON 9 MAY 2017 THE SPONSOR AGREED TO RELAX THE
SCREENING CRITERIA TO ENABLE INCLUSION OF SUBJECTS WITH A
MINIMUM OF 8 FACIAL BLEMISHES IN ORDER TO FACILITATE
RECRUITMENT. THIS AMENDMENT HAS NO IMPACT ON THE
STATISTICAL POWER OF THE STUDY AS THE INCLUSION/EXCLUSION
CRITERIA FOR RANDOMISATION ARE UNCHANGED.

Male subjects are excluded from this study to avoid the confounding impact of facial shaving on clinical assessments. Adolescent subjects and subjects older than 45 years are excluded as they do not represent the target population for the product.

Subjects with a history of using a medicated acne treatment within the last 24 months and subjects who, in the opinion of the investigator, require medicated acne treatment will not be enrolled in the study as they do not represent the target population for the cosmetic products.

Therefore, approximately 200 female subjects aged 18-45 with self-assessed sensitive skin and a minimum of 10 8 and a maximum of 25 facial blemishes (papules and pustules, excluding the nose) will be screened to randomise 132 healthy subjects, to ensure approximately 40 subjects in the test product regimen, 40 subjects in the no treatment regimen and 40 subjects in the positive control regimen complete the study (assuming a 10% dropout rate). Randomisation will be stratified by age (<21 years old, \geq 21 years of age).

A 5-7 day washout period is included to standardize subjects' cleansing and skin care regimens prior to entering the test phase. Subjects will be instructed not to use any skin care or cosmetic product during the washout phase and to cleanse twice a day (morning and night) with the washout facial cleanser provided (Simple Kind to Skin Moisturising Facial Wash; Commercially Available (UK)). To remain eligible for this study, subjects must complete the washout period (assessed at Visit 2) with at least 8 blemishes (papules and pustules, excluding the nose).

Document Name	Rainbow Clinical Protocol.doc		
Туре	Version	Document Identifier	Effective Date
eldo controlled	4.0; Most-Recent; Effective; CURRENT	090032d580d464b0	23-May-2017 08:33:00
Reason For Issue	Auto Issue		

Following the washout period, subjects who continue to be eligible for the study will be randomised to one of three treatment regimens (no treatment + standard cleanser, test product + standard cleanser, or positive control cream + positive control cleanser). Due to the natural fluctuations of facial blemishes, the negative control, notreatment regimen, is included to provide an anchor for efficacy assessments. All efficacy comparisons of the test product will be to the no-treatment regimen.

A cosmetic moisturising cream with niacinamide reported efficacious in subjects with blemish-prone skin (Vivatinell Acnecinamide Gel Cream) and a cosmetic cleanser containing 2% Salicylic Acid for exfoliation (Neutrogena Visibly Clear Spot Clearing Facial Wash) comprise a positive control regimen to support validation of the clinical study. No statistical comparison between the positive control regimen and the test product is planned.

The test product and no treatment regimens include a standard cleanser (Simple Kind to Skin Moisturising Facial Wash) that has not been designed to deliver improvements in the appearance of blemishes to enable the efficacy of the test product to be accurately evaluated.

During the test phase, subjects randomised to test product or positive control regimen will be instructed to use the cleanser and test/control products twice a day (morning and night). Subjects randomised to the no treatment regimen will use the standard cleanser (only) twice a day. The first application of the standard cleanser or positive control cleanser will be at the site, under supervision of the Investigator or designee who will provide instruction on how to correctly apply the product. The first application of test product or positive control will be conducted by the subject at the site, after cleansing, under the supervision of the Investigator or designee who will provide instruction on how to correctly apply the product.

Blinded evaluator and instrumental assessments will be taken after the washout period (baseline) and after 7, 28 and 56 days of twice-daily product use. All reasonable efforts will be made to ensure the same Evaluator assesses the same subject at each visit.

The Investigator or designee will dispense a diary to all subjects to monitor and encourage compliance. This diary will be reviewed at each site visit by the Investigator or designee and missed/extra applications recorded as deviations. The Investigator or designee will observe the subject applying the products and, if needed, will instruct the subject how to correctly apply them.

Document Name	Rainbow Clinical Protocol.doc		
Туре	Version	Document Identifier	Effective Date
eldo controlled	4.0; Most-Recent; Effective; CURRENT	090032d580d464b0	23-May-2017 08:33:00
Reason For Issue	Auto Issue		

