6.2.6. Subject Eligibility

Subjects meeting the inclusion and exclusion criteria detailed in Appendix 2 and who are otherwise considered eligible to continue in the study by the Investigator or medically qualified designee will be randomised. Confirmation of whether a subject was randomised, or not, will be recorded on the eCRF.

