9. STATISTICAL CONSIDERATIONS AND DATA ANALYSES

9.1 Sample Size Determination

Approximately 200 female subjects aged 18-45 with self-assessed sensitive skin and a minimum of $10 \ 8$ and a maximum of 25 facial blemishes (papules and pustules, excluding the nose) will be screened to randomise 132 healthy subjects, to ensure approximately 40 subjects in the test product regimen, 40 subjects in the no treatment regimen and 40 subjects in the positive control regimen complete the study (Assuming a 10% dropout rate). Randomisation will be stratified by age (<21 years old, ≥ 21 years of age).

The sample size was based on clinical considerations. In a previous study of a cosmetic product, counts of papules and pustules decreased from a baseline mean of 27.6 to a mean of 13.5 at Week 8 (ref. Shalita 1995 IJD). With 40 subjects in both the test product and no-treatment regimens, a difference between groups at least 60% the magnitude of the standard deviation (assumed equal for both groups) would be detectable at two-sided alpha=0.05 with approximately 80% power.

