5. SKIN TYPE

A. Minimum of 10 8 and maximum of 25 blemishes (papules and pustules) at Visit 1 and a minimum of 8 blemishes (papules and pustules) at Visit 2.

Exclusion Criteria

A subject will not be considered still eligible for inclusion in this study if any of the following criteria apply:

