4.5 Analysis of Secondary Objectives

4.5.1 Efficacy

The change from baseline in corneometer measurements at 1 and 3 hours following the first product application as well as at Weeks 1, 4 and 8 will be analysed at each post-baseline time point using the same ANCOVA model as in primary analysis. Differences between least squares means for (i) test product and no treatment regimen; (ii) positive control and no treatment regimen will be presented, together with 95% confidence intervals. The normality assumption for ANCOVA will be checked. If violated, non-parametric method such as Wilcoxon rank sum test may be applied.

The sebumeter and sebumeter excretion rate changes from baseline at Weeks 1, 4 and 8 will be analysed at each post-baseline visit using ANCOVA with treatment main effect, age stratum (<21, ≥21 years of age) and baseline count as covariate. Differences between least squares means for (i) test product and no treatment regimen; (ii) positive control and no treatment regimen will be presented, together with 95% confidence intervals (Table 14.2.3.1 for sebumeter, Table 14.2.4.1 for sebumeter excretion rate). The normality assumption for ANCOVA will be checked. If violated, non-parametric method such as Wilcoxon rank sum test may be applied.

Clinical assessment of blemish counts (papules and pustules) change from baseline at Weeks 1, 4 and 8 will be analysed at each post-baseline visit using ANCOVA with treatment main effect, age stratum (<21, ≥21 years of age) and baseline count as covariate. Differences between least squares means for (i) test product and no treatment regimen; (ii) positive control and no treatment regimen will be presented, together with 95% confidence intervals (Table 14.2.5.1 for the ITT population and Table 14.2.5.4 for the PP population). The normality assumption for ANCOVA will be checked. If violated, non-parametric method such as Wilcoxon rank sum test may be applied. A figure will be provided for blemish profile of the ITT population (Figure 14.2.1).

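### Protocol 3.4 says Amendment 5 leaves power untouched because randomisation criteria did not change, but the Visit 1 limb of criterion 5A did; separately, the Visit 1 blemish count is an unused covariate

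*Protocol*

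**What the plan says.** The note in Protocol 3.4 is current text, not an entry in the amendment table. It records that the screening minimum was relaxed to 8 facial blemishes and states: "THIS AMENDMENT HAS NO IMPACT ON THE" power of the study, because the criteria for randomisation are the same as before.

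Criterion 5A, repeated in Appendix 2, reads: "Minimum of 10 8 and maximum of 25 blemishes (papules and pustules) at Visit 1". The 10 is the deleted figure and the 8 its replacement. The same criterion adds a minimum of 8 at Visit 2. Section 6.2.6 makes Appendix 2 the gate: "Subjects meeting the inclusion and exclusion criteria detailed in Appendix 2" are the ones randomised. Section 5.7.1 likewise requires every criterion to be met.

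Section 3.4 also gives the purpose of the Visit 1 limits: "To account for natural fluctuations in blemish counts, subjects will only be enrolled into the washout phase" if their count lies within them.

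For the analysis, SAP 4.5.1 says that blemish-count change "will be analysed at each post-baseline visit using ANCOVA" with treatment, age stratum and baseline count. SAP 3.1 defines baseline as the last value before product use, which is Visit 2. The Visit 1 count appears in no model, although Protocol 6.1.5 has it recorded and totalled on the CRF.

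**The concern.** The reason given for the power statement does not match the eligibility criteria. A subject with 8 or 9 blemishes at Visit 1 could not be randomised before Amendment 5 and now can, so the randomised population has changed. Protocol 9.2 says the results will feed sample size projections for future studies. A reader planning the next trial needs to know which population the blemish variances and effects describe, and that nobody examined what the lower minimum does to them.

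The blemish model also leaves a second pre-treatment measurement of the outcome unused. Blemish counts fluctuate, as section 3.4 says, so one baseline count measures a subject's underlying level with error and a second count carries further information.

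**Working it through.** **1. Which criteria changed.** Visit 1 minimum in 5A: 10 before, 8 now. Visit 1 maximum: 25, unchanged. Visit 2 minimum: 8, unchanged (also sections 3.4 and 5.2). Sections 5.7.1 and 6.2.6 require both limbs of 5A for randomisation. The reason in section 3.4 is therefore true of the Visit 2 limb only.

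**2. The plan's own power figure.** Protocol 9.1: "With 40 subjects in both the test product and no-treatment regimens", a difference of 0.6 SD "would be detectable at two-sided alpha=0.05 with approximately 80% power". By the normal approximation:

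- Power = Φ(0.6·√(40/2) − 1.960) = Φ(2.683 − 1.960) = 76.5% (75.5% by noncentral t).
- At 44 per arm (132/3 randomised): Φ(0.6·√22 − 1.960) = 80.4%.
- Difference detectable with 80% power at 40 per arm: (1.960 + 0.842)·√(2/40) = 0.626 SD.

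So 80% is met at the number randomised, or by rounding 0.626 to 0.6, but not exactly at 40. That is a separate matter. The inputs here are n, alpha and a difference in SD units. No blemish count or blemish SD enters, so the figure is the same before and after the amendment.

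**3. Blemish counts, assumed inputs.** The documents give no SD or distribution for blemish counts under these entry limits. I assume:

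- gamma-distributed subject means (mean 10 with shape 3, or mean 14 with shape 4);
- count variance equal to the mean or twice it;
- a 20% proportional effect or a fixed effect of 2.5 lesions;
- entry limits as in 5A, 3 million subjects simulated per setting before the limits are applied;
- ANCOVA on the Visit 2 count, age stratum omitted.

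Power at 40 per arm = Φ(d/(s·√(2/40)) − 1.960), with d the adjusted difference and s the residual SD. Example (first row): 2.865/(4.471 × 0.2236) = 2.866, giving Φ(0.906) = 81.7% at minimum 10; 2.712/(4.396 × 0.2236) = 2.759, giving Φ(0.799) = 78.8% at minimum 8.

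| Mean, var/mean, effect | Min 10: d, s, power | Min 8: d, s, power | Min 8 plus Visit 1 count: s, power | Variance cut | Gain at min 8 / min 10 (points) |
|---|---|---|---|---|---|
| 10, 1, 20% | 2.865, 4.471, 81.7% | 2.712, 4.396, 78.8% | 4.141, 83.4% | 11.3% | 4.6 / 3.6 |
| 10, 1, 2.5 | 2.519, 4.642, 68.0% | 2.489, 4.565, 68.4% | 4.261, 74.2% | 12.9% | 5.8 / 4.7 |
| 10, 2, 20% | 2.863, 6.081, 55.8% | 2.743, 5.983, 53.6% | 5.790, 56.2% | 6.3% | 2.6 / 2.2 |
| 10, 2, 2.5 | 2.509, 6.297, 42.9% | 2.506, 6.199, 44.0% | 5.968, 46.8% | 7.3% | 2.9 / 2.1 |
| 14, 1, 20% | 3.172, 4.715, 85.3% | 3.046, 4.665, 83.1% | 4.398, 87.2% | 11.1% | 4.1 / 3.2 |
| 14, 1, 2.5 | 2.493, 4.909, 62.2% | 2.494, 4.866, 63.0% | 4.549, 68.9% | 12.6% | 5.9 / 4.9 |
| 14, 2, 20% | 3.228, 6.455, 60.9% | 3.109, 6.375, 58.8% | 6.173, 61.4% | 6.2% | 2.6 / 2.2 |
| 14, 2, 2.5 | 2.483, 6.720, 37.9% | 2.498, 6.633, 39.1% | 6.390, 41.5% | 7.2% | 2.4 / 2.0 |

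Variance cut = 1 − (s with Visit 1 count / s without)², for example 1 − (4.141/4.396)² = 11.3%.

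**4. Reading the table.**

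- Subjects with 8–9 blemishes at Visit 1 are 12–18% of those randomised.
- Residual SD falls by 0.9–1.7% in all eight settings when the minimum drops to 8.
- Power falls 2.1–3.0 points with a proportional effect, because d is smaller, and rises 0.4–1.2 points with a fixed effect.
- The Visit 1 covariate leaves d essentially as it was (2.712 and 2.713 in the first row) and lowers s at either minimum.

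Further runs with shapes up to 6 and a 22% reduction gave variance cuts of about 4–12% and gains of about 2–4 points.

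**The case against.** The sponsor's note can be defended as loosely worded. It probably meant the Visit 2 minimum, which did not change. The only power statement is in SD units, the primary endpoint is 8-hour Corneometer change with no stated link to blemish count, and the blemish figures quoted in section 9.1 do not enter the calculation. All of this stands. It means that the stated reason is wrong, not that the planned power changed.

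A reader might infer more: that the amendment cost precision on blemish counts, and that adjusting for the Visit 1 count would win it back. The documents do not support that. Residual SD goes down slightly at the lower minimum. A power loss appears only if the effect is assumed proportional. Section 3.4 does describe an effect on the rate of new blemishes at steady state, which leans that way, but no effect model is specified. The covariate cannot restore a smaller absolute difference, and it would have helped under the old threshold too.

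Nor does extra regression to the mean bias the comparison. It is equal in expectation across randomised arms, and section 3.4 includes the no-treatment arm because of natural fluctuation. In the simulations the added untreated drift is about 0.1–0.2 counts.

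Finally, omitting a second baseline is no error in a proof-of-concept study that treats p-values mainly as summary statistics. I agree; the covariate is offered as an improvement.

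**Conclusion.** The contradiction between section 3.4 and criterion 5A follows from the documents alone. The Visit 1 minimum applied at randomisation was lowered from 10 to 8, so the reason given for unchanged power is incorrect. The 0.6 SD power figure and the Corneometer primary are untouched. For the secondary blemish counts, absence of any impact is unassessed rather than disproved: the simulated change runs from −3.0 to +1.2 points, and its sign depends on the effect model.

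The firmer practical gain is the unused Visit 1 count, which helped in every setting examined. The sizes rest on assumed means, shapes, dispersion and effects. The gain is smaller when counts vary more around a subject's own mean.

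**What to change.** 1. Reword the note in Protocol 3.4 to say four things: the Visit 2 minimum of 8 is unchanged; the Visit 1 minimum in criterion 5A, required for randomisation, was lowered from 10 to 8; planned power in SD units does not depend on this; the effect on blemish counts was not assessed. Cost: a sentence or two.
2. Separately, in the blemish-count ANCOVA of SAP 4.5.1, add the Visit 1 blemish count as a second covariate beside the Visit 2 count. Present it as an efficiency gain, not as recovery of anything lost through the amendment. Cost: one degree of freedom and one model term, using data already on the eCRF. The SAP addendum of 20 December 2017 already postdates unblinding, so if the covariate is added at that stage, keep the planned model as the main blemish analysis and label the extended one a sensitivity analysis.

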4. SELECTION OF STUDY POPULATION AND WITHDRAWAL CRITERIA

Specific information regarding warnings, precautions, contraindications, adverse events, and other pertinent information on the GSK investigational product or other study treatment that may impact subject eligibility is provided in the safety statement.

Deviations from inclusion and exclusion criteria are not allowed because they can potentially jeopardize the scientific integrity of the study, regulatory acceptability or subject safety. Therefore, adherence to the criteria as specified in the protocol is essential.

4.1. Inclusion Criteria

A subject will be eligible for inclusion in this study only if all of the following criteria apply:

1. CONSENT

Demonstrates understanding of the study procedures, restrictions and willingness to participate as evidenced by voluntary written informed consent and has received a signed and dated copy of the informed consent form.

2. SEX / AGE

Female aged between 18 and 45 years inclusive.

3. GENERAL HEALTH

Good general and mental health with, in the opinion of the investigator or medically qualified designee no clinically significant and relevant abnormalities in medical history or upon physical examination.

4. COMPLIANCE

Willingness to actively participate in the study and to attend all scheduled visits.

5. SKIN TYPE

- A. Minimum of 10 8 and maximum of 25 blemishes (papules and pustules) at Visit 1 and a minimum of 8 blemishes (papules and pustules) at Visit 2.
- B. Fitzpatrick photo-type I-V (Appendix 1 SECTION 6.1.4).
- C. Sebumeter score of $>66 \mu g / cm^2$ at the forehead.

6. CONTRACEPTION

Document Name	Rainbow Clinical Protocol.doc		
Туре	Version	Document Identifier	Effective Date
eldo controlled	4.0; Most-Recent; Effective; CURRENT	090032d580d464b0	23-May-2017 08:33:00
Reason For Issue	Auto Issue		

Females of childbearing potential who are, in the opinion of the investigator, practising a reliable method of contraception. Adequate contraception is defined as abstinence, oral contraceptive, either combined or progestogen alone OR injectable progestogen OR implants of levonorgestrel OR estrogenic vaginal ring OR percutaneous contraceptive patches OR intrauterine device or intrauterine system OR double barrier method (condom or occlusive cap [diaphragm or cervical vault caps] plus spermicidal agent [foam, gel, film, cream, suppository]) OR male partner sterilization prior to the female subject's entry into the study, and this male is the sole partner for that subject.

7. Cleansing Routine

Cleanses their face at least once a day.

